**Table 45: Number of Subjects with Medically-Attended AEs (MAAEs) by Severity throughout the Study Period**

	All (N = 120)	COVIVAC				Placebo (N = 20)
		1 µg (N = 25)	3 µg (N = 25)	10 µg (N = 25)	1 µg + CpG (N = 25)	
with one or more MAAEs by severity*	xx (xx.x%)	xx (xx.x%)	xx (xx.x%)	xx (xx.x%)	xx (xx.x%)	xx (xx.x%)
Grade1 (Mild)	xx (xx.x%)	xx (xx.x%)	xx (xx.x%)	xx (xx.x%)	xx (xx.x%)	xx (xx.x%)
Grade2 (Moderate)	xx (xx.x%)	xx (xx.x%)	xx (xx.x%)	xx (xx.x%)	xx (xx.x%)	xx (xx.x%)
Grade3 (Severe)	xx (xx.x%)	xx (xx.x%)	xx (xx.x%)	xx (xx.x%)	xx (xx.x%)	xx (xx.x%)
Grade4 (Potentially life-threatening)	xx (xx.x%)	xx (xx.x%)	xx (xx.x%)	xx (xx.x%)	xx (xx.x%)	xx (xx.x%)
with no MAAE	xx (xx.x%)	xx (xx.x%)	xx (xx.x%)	xx (xx.x%)	xx (xx.x%)	xx (xx.x%)
with vaccine-related MAAEs by severity*	xx (xx.x%)	xx (xx.x%)	xx (xx.x%)	xx (xx.x%)	xx (xx.x%)	xx (xx.x%)
Grade1 (Mild)	xx (xx.x%)	xx (xx.x%)	xx (xx.x%)	xx (xx.x%)	xx (xx.x%)	xx (xx.x%)
Grade2 (Moderate)	xx (xx.x%)	xx (xx.x%)	xx (xx.x%)	xx (xx.x%)	xx (xx.x%)	xx (xx.x%)
Grade3 (Severe)	xx (xx.x%)	xx (xx.x%)	xx (xx.x%)	xx (xx.x%)	xx (xx.x%)	xx (xx.x%)
Grade4 (Potentially life-threatening)	xx (xx.x%)	xx (xx.x%)	xx (xx.x%)	xx (xx.x%)	xx (xx.x%)	xx (xx.x%)
Subjects with specific adverse events						
System Organ Class Term	Preferred Term					
.....	.....	xx (xx.x%)	xx (xx.x%)	xx (xx.x%)	xx (xx.x%)	xx (xx.x%)

Note: “N” is the total number of subject in each group and “xx” represent the value number.

\* Maximum severity grade will be considered.

**Table 46: Number of Subjects with Adverse Events of Special Interest (AESI) by Severity throughout the Study Period**

	All (N = 120)	COVIVAC				Placebo (N = 20)
		1 µg (N = 25)	3 µg (N = 25)	10 µg (N = 25)	1 µg + CpG (N = 25)	
with one or more AESI by severity*	xx (xx.x%)	xx (xx.x%)	xx (xx.x%)	xx (xx.x%)	xx (xx.x%)	xx (xx.x%)
Grade1 (Mild)	xx (xx.x%)	xx (xx.x%)	xx (xx.x%)	xx (xx.x%)	xx (xx.x%)	xx (xx.x%)
Grade2 (Moderate)	xx (xx.x%)	xx (xx.x%)	xx (xx.x%)	xx (xx.x%)	xx (xx.x%)	xx (xx.x%)
Grade3 (Severe)	xx (xx.x%)	xx (xx.x%)	xx (xx.x%)	xx (xx.x%)	xx (xx.x%)	xx (xx.x%)
Grade4 (Potentially life-threatening)	xx (xx.x%)	xx (xx.x%)	xx (xx.x%)	xx (xx.x%)	xx (xx.x%)	xx (xx.x%)
with no AESI	xx (xx.x%)	xx (xx.x%)	xx (xx.x%)	xx (xx.x%)	xx (xx.x%)	xx (xx.x%)
with vaccine-related AESI by severity*	xx (xx.x%)	xx (xx.x%)	xx (xx.x%)	xx (xx.x%)	xx (xx.x%)	xx (xx.x%)
Grade1 (Mild)	xx (xx.x%)	xx (xx.x%)	xx (xx.x%)	xx (xx.x%)	xx (xx.x%)	xx (xx.x%)
Grade2 (Moderate)	xx (xx.x%)	xx (xx.x%)	xx (xx.x%)	xx (xx.x%)	xx (xx.x%)	xx (xx.x%)
Grade3 (Severe)	xx (xx.x%)	xx (xx.x%)	xx (xx.x%)	xx (xx.x%)	xx (xx.x%)	xx (xx.x%)
Grade4 (Potentially life-threatening)	xx (xx.x%)	xx (xx.x%)	xx (xx.x%)	xx (xx.x%)	xx (xx.x%)	xx (xx.x%)
Subjects with specific adverse events						
System Organ Class Term	Preferred Term					
.....	.....	xx (xx.x%)	xx (xx.x%)	xx (xx.x%)	xx (xx.x%)	xx (xx.x%)

**Note:** “N” is the total number of subject in each group and “xx” represent the value number.

\* Maximum severity grade will be considered.

**Table 47: Number of Subjects with Adverse Events of Special Interest (AESI) Relevant to COVID-19 by Severity throughout the Study Period**

	All (N = 120)	COVIVAC				Placebo (N = 20)
		1 µg (N = 25)	3 µg (N = 25)	10 µg (N = 25)	1 µg + CpG (N = 25)	
with one or more AESIs relevant to COVID-19 by severity*	xx (xx.x%)	xx (xx.x%)	xx (xx.x%)	xx (xx.x%)	xx (xx.x%)	xx (xx.x%)
Grade1 (Mild)	xx (xx.x%)	xx (xx.x%)	xx (xx.x%)	xx (xx.x%)	xx (xx.x%)	xx (xx.x%)
Grade2 (Moderate)	xx (xx.x%)	xx (xx.x%)	xx (xx.x%)	xx (xx.x%)	xx (xx.x%)	xx (xx.x%)
Grade3 (Severe)	xx (xx.x%)	xx (xx.x%)	xx (xx.x%)	xx (xx.x%)	xx (xx.x%)	xx (xx.x%)
Grade4 (Potentially life-threatening)	xx (xx.x%)	xx (xx.x%)	xx (xx.x%)	xx (xx.x%)	xx (xx.x%)	xx (xx.x%)
with no AESI relevant to COVID-19	xx (xx.x%)	xx (xx.x%)	xx (xx.x%)	xx (xx.x%)	xx (xx.x%)	xx (xx.x%)
with vaccine-related AESI by severity*	xx (xx.x%)	xx (xx.x%)	xx (xx.x%)	xx (xx.x%)	xx (xx.x%)	xx (xx.x%)
Grade1 (Mild)	xx (xx.x%)	xx (xx.x%)	xx (xx.x%)	xx (xx.x%)	xx (xx.x%)	xx (xx.x%)
Grade2 (Moderate)	xx (xx.x%)	xx (xx.x%)	xx (xx.x%)	xx (xx.x%)	xx (xx.x%)	xx (xx.x%)
Grade3 (Severe)	xx (xx.x%)	xx (xx.x%)	xx (xx.x%)	xx (xx.x%)	xx (xx.x%)	xx (xx.x%)
Grade4 (Potentially life-threatening)	xx (xx.x%)	xx (xx.x%)	xx (xx.x%)	xx (xx.x%)	xx (xx.x%)	xx (xx.x%)
Subjects with specific adverse events						
System Organ Class Term	Preferred Term					
.....	.....	xx (xx.x%)	xx (xx.x%)	xx (xx.x%)	xx (xx.x%)	xx (xx.x%)

**Note:** “N” is the total number of subject in each group and “xx” represent the value number

\* Maximum severity grade will be considered.

**Table 48: Number of Subjects with Adverse Events of Potential Immune-Mediated Medical Conditions (PIMMC) by Severity throughout the Study Period**

	All (N = 120)	COVIVAC				Placebo (N = 20)
		1 µg (N = 25)	3 µg (N = 25)	10 µg (N = 25)	1 µg + CpG (N = 25)	
with one or more AEs of PIMMC by severity*	xx (xx.x%)	xx (xx.x%)	xx (xx.x%)	xx (xx.x%)	xx (xx.x%)	xx (xx.x%)
Grade1 (Mild)	xx (xx.x%)	xx (xx.x%)	xx (xx.x%)	xx (xx.x%)	xx (xx.x%)	xx (xx.x%)
Grade2 (Moderate)	xx (xx.x%)	xx (xx.x%)	xx (xx.x%)	xx (xx.x%)	xx (xx.x%)	xx (xx.x%)
Grade3 (Severe)	xx (xx.x%)	xx (xx.x%)	xx (xx.x%)	xx (xx.x%)	xx (xx.x%)	xx (xx.x%)
Grade4 (Potentially life-threatening)	xx (xx.x%)	xx (xx.x%)	xx (xx.x%)	xx (xx.x%)	xx (xx.x%)	xx (xx.x%)
with no AE of PIMMC	xx (xx.x%)	xx (xx.x%)	xx (xx.x%)	xx (xx.x%)	xx (xx.x%)	xx (xx.x%)
with vaccine-related AEs of PIMMC by severity*	xx (xx.x%)	xx (xx.x%)	xx (xx.x%)	xx (xx.x%)	xx (xx.x%)	xx (xx.x%)
Grade1 (Mild)	xx (xx.x%)	xx (xx.x%)	xx (xx.x%)	xx (xx.x%)	xx (xx.x%)	xx (xx.x%)
Grade2 (Moderate)	xx (xx.x%)	xx (xx.x%)	xx (xx.x%)	xx (xx.x%)	xx (xx.x%)	xx (xx.x%)
Grade3 (Severe)	xx (xx.x%)	xx (xx.x%)	xx (xx.x%)	xx (xx.x%)	xx (xx.x%)	xx (xx.x%)
Grade4 (Potentially life-threatening)	xx (xx.x%)	xx (xx.x%)	xx (xx.x%)	xx (xx.x%)	xx (xx.x%)	xx (xx.x%)
Subjects with specific adverse events						
System Organ Class Term	Preferred Term					
.....	.....	xx (xx.x%)	xx (xx.x%)	xx (xx.x%)	xx (xx.x%)	xx xx.xx  %)

**Note:** “N” is the total number of subject in each group and “xx” represent the value number.

\* Maximum severity grade will be considered.

**Table 49: Duration Days of Adverse Event During First 28 Days Post Vaccination by Severity Grade**

Severity	All (N = 120)	COVIVAC				Placebo (N = 20)
	1 µg (N = 25)	3 µg (N = 25)	10 µg (N = 25)	1 µg + CpG (N = 25)		
AE During the first 28 days post –first vaccination	All, Mean of days (SD)					
	Mild					
	Moderate					
	Severe					
	Potentially life-threatening					
	Related, Mean of days (SD)					
	Mild					
	Moderate					
	Severe					
	Potentially life-threatening					
AE During the first 28 days post – second vaccination	All, Mean of days (SD)					
	Mild					
	Moderate					
	Severe					
	Potentially life-threatening					
	Related, Mean of days (SD)					
	Mild					
	Moderate					
	Severe					
	Potentially life-threatening					

**Table 49: Duration Days of Adverse Event During First 28 Days Post Vaccination by Severity Grade (continued)**

Severity	All (N = 120)	COVIVAC				Placebo (N = 20)
		1 µg (N = 25)	3 µg (N = 25)	10 µg (N = 25)	1 µg + CpG (N = 25)	
SAE During the first 28 days post – first vaccination	All, Mean of days (SD)					
	Mild					
	Moderate					
	Severe					
	Potentially life-threatening					
	Related, Mean of days (SD)					
	Mild					
	Moderate					
	Severe					
	Potentially life-threatening					
SAE During the first 28 days post – second vaccination	All, Mean of days (SD)					
	Mild					
	Moderate					
	Severe					
	Potentially life-threatening					
	Related, Mean of days (SD)					
	Mild					
	Moderate					
	Severe					
	Potentially life-threatening					

**Table 49: Duration Days of Adverse Event During First 28 Days Post Vaccination by Severity Grade (continued)**

Severity	All (N = 120)	COVIVAC				Placebo (N = 20)
		1 µg (N = 25)	3 µg (N = 25)	10 µg (N = 25)	1 µg + CpG (N = 25)	
MAAE During the first 28 days post – first injection	All, Mean of days (SD)					
	Mild					
	Moderate					
	Severe					
	Potentially life-threatening					
	Related, Mean of days (SD)					
	Mild					
	Moderate					
	Severe					
	Potentially life-threatening					
MAAE During the first 28 days post – second injection	All, Mean of days (SD)					
	Mild					
	Moderate					
	Severe					
	Potentially life-threatening					
	Related, Mean of days (SD)					
	Mild					
	Moderate					
	Severe					
	Potentially life-threatening					

**Table 49: Duration Days of Adverse Event During First 28 Days Post Vaccination by Severity Grade (continued)**

	Severity	All (N = 120)	COVIVAC				Placebo (N = 20)
			1 µg (N = 25)	3 µg (N = 25)	10 µg (N = 25)	1 µg + CpG (N = 25)	
AESI During the first 28 days post – first injection	All, Mean of days (SD)						
	Mild						
	Moderate						
	Severe						
	Potentially life-threatening						
	Related, Mean of days (SD)						
	Mild						
	Moderate						
	Severe						
	Potentially life-threatening						
AESI During the first 28 days post – second injection (Visit 6 (Day 57))	All, Mean of days (SD)						
	Mild						
	Moderate						
	Severe						
	Potentially life-threatening						
	Related, Mean of days (SD)						
	Mild						
	Moderate						
	Severe						
	Potentially life-threatening						

**Table 50: Summary of Adverse Events during the First 28 days after each Vaccination by MedDRA term**

System Organ Class (SOC)	Preferred Term (PT)	All (N = xx)		COVIVAC				1 µg + CpG (N = 25)		Placebo (N = 20)	
		NE	n (%)	NE	n (%)	NE	n (%)	NE	n (%)	NE	n (%)
Overall											
All SOC	All PT										
SOC 1	All PT 1 PT 2										
SOC 2	All PT 1 PT 2										
1st dose											
All SOC	All PT										
SOC 1	All PT 1 PT 2										
SOC 2	All PT 1 PT 2										
2nd dose											
All SOC	All PT										
SOC 1	All PT 1 PT 2										
SOC 2	All PT 1 PT 2										

**Note:** “N” is the total number of patient in each group and “xx” represent the value number.

“NE” is number of events.

“n” is number of subject who has at least one adverse event.

**Table 51: Summary of Serious Adverse Events throughout the Entire Study Period by MedDRA term**

System Organ Class (SOC)	Preferred Term (PT)	All (N = xx)		COVIVAC								Placebo (N = 20)
				1 µg (N = 25)		3 µg (N = 25)		10 µg (N = 25)		1 µg + CpG (N = 25)		
		NE	n (%)	NE	n (%)	NE	n (%)	NE	n (%)	NE	n (%)	
All SOC	All PT											
SOC 1	All											
	PT 1											
	PT 2											
SOC 2	All											
	PT 1											
	PT 2											

**Note:** "N" is the total number of patient in each group and "xx" represent the value number.

"NE" is number of events.

"n" is number of subject who has at least one adverse event.

**Table 52: Summary of Serious Adverse Event during the First 28 days after each Vaccination by Criteria**

Criteria	All (N = 120)		COVIVAC				Placebo (N = 20)		
	NE	n (%)	1 µg (N = 25)	3 µg (N = 25)	10 µg (N = 25)	1 µg + CpG (N = 25)	NE	n (%)	
Overall									
All									
Results in death									
Is life-threatening									
Requires inpatient hospitalization or prolongation of an existing hospitalization									
Results in persistent or significant disability or incapacity									
Results in a congenital anomaly or birth defect									
Is medically significant									
1st dose									
All									
Results in death									
Is life-threatening									
Requires inpatient hospitalization or prolongation of an existing hospitalization									
Results in persistent or significant disability or incapacity									
Results in a congenital anomaly or birth defect									
Is medically significant									
2nd dose									
All									
Results in death									
Is life-threatening									

Criteria	COVIVAC					Placebo (N = 20)				
	All (N = 120)		1 µg (N = 25)	3 µg (N = 25)	10 µg (N = 25)					
	NE	n (%)	NE	n (%)	NE	n (%)	NE	n (%)	NE	n (%)
Requires inpatient hospitalization or prolongation of an existing hospitalization										
Results in persistent or significant disability or incapacity in a congenital anomaly or birth defect										
Is medically significant										

**Note:** NE – Number of events

n (%) – Number of subject and percentage

**Table 53: Summary of Serious Adverse Event throughout the Study Period by Criteria**

Criteria	COVIVAC					Placebo (N = 20)				
	All (N = 120)		1 µg (N = 25)	3 µg (N = 25)	10 µg (N = 25)					
	NE	n (%)	NE	n (%)	NE	n (%)	NE	n (%)	NE	n (%)
All										
Results in death										
Is life-threatening										
Requires inpatient hospitalization or prolongation of an existing hospitalization										
Results in persistent or significant disability or incapacity in a congenital anomaly or birth defect										
Is medically significant										

**Note:** NE – Number of events

n (%) – Number of subject and percentage

**Table 54: Summary of Adverse Event by Outcome during the First 28 Days after each Vaccination**

Outcome	All (N = xx)		COVIVAC				Placebo (N = 20)	
	NE	n (%)	1 µg (N = 25)	3 µg (N = 25)	10 µg (N = 25)	1 µg + CpG (N = 25)	NE	n (%)
Overall								
All								
Ongoing								
Recovered/Resolved								
Recovered/Resolved with sequelae								
Fatal								
Unknown								
1st Dose								
All								
Ongoing								
Recovered/Resolved								
Recovered/Resolved with sequelae								
Fatal								
Unknown								
2nd Dose								
All								
Ongoing								
Recovered/Resolved								
Recovered/Resolved with sequelae								
Fatal								
Unknown								

**Table 55: Summary of Serious Adverse Event by Outcome throughout the Study Period**

Outcome	All (N = xx)		COVIVAC				Placebo (N = 20)	
	NE	n (%)	1 µg (N = 25)	3 µg (N = 25)	10 µg (N = 25)	1 µg + CpG (N = 25)	NE	n (%)
All								
Ongoing								
Recovered/Resolved								
Recovered/Resolved with sequelae								
Fatal								
Unknown								

**Table 56: Summary of Adverse Event during the First 28 Days after each Vaccination by Relationship to Study Vaccine**

Relationship to Study Vaccine	All (N = xx)		COVIVAC				Placebo (N = 20)	
			1 µg (N = 25)	3 µg (N = 25)	10 µg (N = 25)	1 µg + CpG (N = 25)		
	NE	n (%)	NE	n (%)	NE	n (%)	NE	n (%)
Overall								
All								
Related								
Not related								
1st Dose								
All								
Related								
Not related								
2nd Dose								
All								
Related								
Not related								

**Table 57: Summary of Serious Adverse Event throughout the Study Period by Relationship to Study Vaccine**

Relationship to Study Vaccine	All (N = xx)		COVIVAC				Placebo (N = 20)	
			1 µg (N = 25)	3 µg (N = 25)	10 µg (N = 25)	1 µg + CpG (N = 25)		
	NE	n (%)	NE	n (%)	NE	n (%)	NE	n (%)
All								
Related								
Not related								

**Table 58: Summary of Adverse event by Action Taken to the Study Vaccine during the First 28 Days after each Vaccination**

Action Taken to the Study Vaccine	COVIVAC					Placebo (N = 20)			
	All (N = xx)	1 µg (N = 25)	3 µg (N = 25)	10 µg (N = 25)	1 µg + CpG (N = 25)				
NE	n (%)	NE	n (%)	NE	n (%)	NE	n (%)	NE	n (%)
Overall									
All									
Withdrawn									
Delayed									
Continued									
Not applicable									
1st Dose									
All									
Withdrawn									
Delayed									
Continued									
Not applicable									
2nd Dose									
All									
Withdrawn									
Delayed									
Continued									
Not applicable									

**Table 59: Summary of Serious Adverse Event by Action Taken to the Study Vaccine throughout the Study Period**

Action Taken to the Study Vaccine	COVIVAC										Placebo (N = 20)	
	All (N = xx)		1 µg (N = 25)		3 µg (N = 25)		10 µg (N = 25)		1 µg + CpG (N = 25)			
	NE	n (%)	NE	n (%)	NE	n (%)	NE	n (%)	NE	n (%)	NE	n (%)
All												
Withdrawn												
Delayed												
Continued												
Not applicable												

**Note:** NE: Number of events

n: Number of subject with at least one AE / %: (n/N)\*100

## Appendix 1.E. Hematology Results

**Table 60: Overall Number of Subjects with Any Abnormal Hematology Results in Safety Analysis Population**

	All (N = 120)	COVIVAC				Placebo (N = 20)
		1 µg (N = 25)	3 µg (N = 25)	10 µg (N = 25)	1 µg + CpG (N = 25)	
Overall, n (%)						
with hemoglobin abnormal result	xx (xx.x%)	xx (xx.x%)	xx (xx.x%)	xx (xx.x%)	xx (xx.x%)	xx (xx.x%)
with WBC abnormal result	xx (xx.x%)	xx (xx.x%)	xx (xx.x%)	xx (xx.x%)	xx (xx.x%)	xx (xx.x%)
with platelet abnormal result	xx (xx.x%)	xx (xx.x%)	xx (xx.x%)	xx (xx.x%)	xx (xx.x%)	xx (xx.x%)
with one or more abnormal result	xx (xx.x%)	xx (xx.x%)	xx (xx.x%)	xx (xx.x%)	xx (xx.x%)	xx (xx.x%)
with no abnormal result	xx (xx.x%)	xx (xx.x%)	xx (xx.x%)	xx (xx.x%)	xx (xx.x%)	xx (xx.x%)
Visit 2 (Day 8)						
with hemoglobin abnormal result						
with WBC abnormal result						
with platelet abnormal result						
with one or more abnormal result						
with no abnormal result						
Visit 4 (Day 36)						
with hemoglobin abnormal result						
with WBC abnormal result						
with platelet abnormal result						
with one or more abnormal result						
with no abnormal result						

**Table 61: Hemoglobin Value at each Follow-up Visit Compared to Baseline**

Hemoglobin (g/dL)	All (N = 120)	COVIVAC				Placebo (N = 20)
		1 µg (N = 25)	3 µg (N = 25)	10 µg (N = 25)	1 µg + CpG (N = 25)	
Baseline						
n	xx	xx	xx	xx	xx	xx
Mean (SD)	xx.xx (xx.xx)	xx.xx (xx.xx)	xx.xx (xx.xx)	xx.xx (xx.xx)	xx.xx (xx.xx)	xx.xx (xx.xx)
Median (q1-q3)	xx (xx-xx)	xx (xx-xx)	xx (xx-xx)	xx (xx-xx)	xx (xx-xx)	xx (xx-xx)
Min-Max	xx-xx	xx-xx	xx-xx	xx-xx	xx-xx	xx-xx
Normal	xx (xx.x%)	xx (xx.x%)	xx (xx.x%)	xx (xx.x%)	xx (xx.x%)	xx (xx.x%)
Abnormal	xx (xx.x%)	xx (xx.x%)	xx (xx.x%)	xx (xx.x%)	xx (xx.x%)	xx (xx.x%)
Mild						
Moderate						
Severe						
Potentially life threatening						
Visit 2 (Day 8)						
n						
Mean (SD)						
Median (q1-q3)						
Min-Max						
*p-value =						
Normal						
Abnormal						
Mild						
Moderate						
Severe						
Potentially life threatening						
**p-value=						

**Table 61: Hemoglobin Value at each Follow-up Visit Compared to Baseline (continued)**

Hemoglobin (g/dL)	All (N = 120)	COVIVAC				Placebo (N = 20)		
		1 µg (N = 25)	3 µg (N = 25)	10 µg (N = 25)	1 µg + CpG (N = 25)			
Change between Day 8 and Baseline								
Mean of % Difference (95% CI)								
Visit 4 (Day 36)								
n								
Mean (SD)								
Median (q1-q3)								
Min-Max								
*p-value =								
Normal								
Abnormal								
Mild								
Moderate								
Severe								
Potentially life threatening								
**p-value=								
Change between Day 36 and Baseline								
Mean of % Difference (95% CI)								

**Note:** + CpG1018 1.5 mg (Adjuvant)

\* P-value based on paired t test/ Wilcoxon signed-rank test

\*\* P-value based on Mc Nemar chi-square test, Normality of results (Normal/Abnormal) will be tested significant difference.

A significance test comparing a baseline (pre-vaccination) with a follow up measurement separately in vaccination group.

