## 8.6. Clinical Laboratory Evaluations

Screening viral serology assessments for Hepatitis B (HBsAg) and Hepatitis C (HCV Ab) will be described as categorical variables on a demographics table ([Table 28](#)).

Clinical safety laboratory values (serum hematology and chemistry) are collected at screening and 7 days post-vaccination for each dose. They will be summarized for the safety analysis population. Hematology and chemistry results evaluated at screening will be summarized as continuous variables by vaccine groups ([Table 24](#) through [Table 27](#)).

Screening and post-vaccination (Day 8 and Day 36) serum hematology and chemistry will be graded by severity. Grade 2 or higher were automatically considered as clinically significant and reported as AE, while Grade 1 abnormalities were subject to investigator opinion.

Continuous summaries of laboratory parameters (Hgb, WBC count, Plt, AST, ALT, total bilirubin, and creatinine) and the change from baseline will be computed by time point (including unscheduled visits, in chronological order) and treatment group, including mean, standard deviation, median, 1st and 3rd quartiles (IQR) and range, for all observations regardless of abnormality status (see [Table 60](#) through [Table 68](#)). Summaries will also be produced presenting the proportion of each severity grading using the number of subjects that provided a sample as denominator, as well as those considered clinically significant, using the maximum severity for a given subject, where relevant. A summary of safety laboratory abnormalities will be prepared by parameter, severity (by grade and any abnormality), and time point. Fisher's exact 2-tailed test will be used to test the differences in abnormality rates across all groups, by time point for scheduled visits, and overall.

Figures will be prepared for each laboratory parameter using boxplots to describe the distribution of values and changes from baseline across visits, by group, incorporating unique points and/or colors for abnormalities ([Figure 2](#) through [Figure 8](#)).

A listing of all lab results will be prepared, in addition to a listing only for abnormalities, and each will include the parameter, study day (Visit), value, units, change from baseline, LLN/ULN, and abnormality grade ([Listing 9A](#), [Listing 9B](#), Appendix 3).

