**Table 20: Serum Toxicity Grading – Protocol Appendix 3**

Serum	Mild (Grade 1)	Moderate (Grade 2)	Severe (Grade 3)	Potentially Life Threatening (Grade 4)
Creatinine (mg/dL)	1.1 – 1.3 x ULN	> 1.3 – 1.8 x ULN OR increase of > 0.3 above baseline	> 1.8 – < 3.5 x ULN OR increase of 1.5 – < 2.0 x above baseline	≥ 3.5 x ULN OR increase of > 2.0 x above baseline
Liver function tests – AST, ALT increased	1.25 – < 2.5 x ULN	2.5 – < 5.0 x ULN	5.0 – < 10.0 x ULN	≥ 10.0 x ULN
Total bilirubin	1.1 – < 1.6 x ULN	1.6 – < 2.6 x ULN	2.6 – < 5.0 x ULN	≥ 5.0 x ULN

Abbreviation: ULN = upper limit of normal range

Note: the laboratory values provided in this table serve as guidelines and are dependent upon institutional normal parameters.

The grading scales for laboratory abnormalities have been derived from *Guidance for Industry, Toxicity Grading Scale for Healthy Adult and Adolescent Volunteers Enrolled in Preventive Vaccine Clinical Trials*, U.S. Department of Health and Human Services, FDA, CBER, September 2007, and the *Division of AIDS (DAIDS) Table for Grading the Severity of Adult and Pediatric Adverse Events* (Version 2.1, July 2017) from the US NIH.

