**Table 21: Hematology Toxicity Grading – Protocol Appendix 3**

Hematology	Mild (Grade 1)	Moderate (Grade 2)	Severe (Grade 3)	Potentially Life Threatening (Grade 4)
Hemoglobin [Female] (g/dL)	11.0 – 12.0	9.5 – 10.9	8.0 – 9.4	< 8.0
Hemoglobin [Male] (g/dL)	12.5 – 13.5	10.5 – 12.4	8.5 – 10.4	< 8.5
OR Hemoglobin, change from baseline value (g/dL)	1.0 – 1.5	1.6 – 2.0	2.1 – 5.0	> 5.0
WBC, increased (cell/mm  )	10,800 – 15,000	15,001 – 20,000	20,001 – 25,000	> 25,000
WBC, decreased (cell/mm  )	2,500 – 3,400	1,500 – 2,499	1,000 – 1,499	< 1,000
Platelets, decreased (cell/mm  )	100,000 – <125,000	50,000 – < 100,000	25,000 – < 50,000	< 25,000

Abbreviation: ULN = upper limit of normal range

Note: the laboratory values provided in this table serve as guidelines and are dependent upon institutional normal parameters.

The grading scales for laboratory abnormalities have been derived from *Guidance for Industry, Toxicity Grading Scale for Healthy Adult and Adolescent Volunteers Enrolled in Preventive Vaccine Clinical Trials*, U.S. Department of Health and Human Services, FDA, CBER, September 2007, and the *Division of AIDS (DAIDS) Table for Grading the Severity of Adult and Pediatric Adverse Events* (Version 2.1, July 2017) from the US NIH.

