**Table 65: Creatinine Value at each Follow-up Visit Compared to Baseline in Safety Analysis Population (continue)**

Creatinine (μmol/L)	All (N = 120)	COVIVAC				Placebo (N = 20)		
		1 μg (N = 25)	3 μg (N = 25)	10 μg (N = 25)	1 μg + CpG (N = 25)			
Change between Day 8 and Baseline								
Mean of % Difference (95% CI)								
Visit 4 (Day 36)								
n								
Mean (SD)								
Median (q1-q3)								
Min-Max								
*p-value =								
Normal								
Abnormal								
Mild								
Moderate								
Severe								
Potentially life threatening								
Change between Day 8 and Baseline								
Mean of % Difference (95% CI)								

**Note:** + CpG1018 1.5 mg (Adjuvant)

\* P-value based on Kruskal Wallis Test

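### No planned test compares change from baseline in a vaccine arm with placebo: haematology and vital signs are tested within arm, chemistry without baseline

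*SAP*

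**What the plan says.** - **Haematology, Tables 61-63.** Continuous values: "P-value based on paired t test/ Wilcoxon signed-rank test". Normal/abnormal status: "P-value based on Mc Nemar chi-square test, Normality of results (Normal/Abnormal) will be tested significant difference". The footnote fixes the comparison: "A significance test comparing a baseline (pre-vaccination) with a follow up measurement separately in vaccination group".
- **Vital signs, Tables 71-80.** The same footnotes appear. Section 8.7 plans only descriptive summaries and mentions no test.
- **Chemistry, Tables 65-68.** "P-value based on Kruskal Wallis Test". The p-value row stands under the follow-up values, not under the change rows. The footnote does not name the groups. Kruskal-Wallis is an independent-samples test, so a comparison of arms is the natural reading.
- **Section 8.6.** For all seven laboratory parameters, Fisher's "exact 2-tailed test will be used to test the differences in abnormality rates across all groups", by scheduled visit and overall. Tables 60 and 64, where the result would naturally go, have neither a p-value row nor a test footnote.
- **Change from baseline.** Sections 8.3.1 and 8.6 plan change summaries by time point, with a mean percentage change and 95% CI for each arm. No difference between arms is defined. Section 6.4 rules out covariates.
- **Labels.** In Tables 65-68 the change row that follows Visit 4 (Day 36) is labelled as Day 8 versus baseline. The haematology shells label the same row correctly. Tables 79-80 give temperature change as a percentage of a value in °C.

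**The concern.** Testing an arm against its own baseline asks whether anything changed, not whether the vaccine changed it. Blood pressure settling after the injection, laboratory drift or time of day moves every arm, placebo included, and a paired test counts that movement as evidence in each vaccine arm. The trial randomises 20 subjects to placebo to separate such shifts from a vaccine effect, but these p-values do not use them. Comparing significance in a vaccine arm with non-significance in placebo does not repair this, because the difference between the two arms is still untested.

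Chemistry has the opposite weakness. Randomisation makes a comparison of follow-up values valid, but ignoring a strongly correlated baseline wastes precision in arms of 20 to 25. Two laboratory panels with the same visits and design are thus analysed in opposite ways, and neither yields the vaccine-versus-placebo contrast of change that a safety reader would want.

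**Working it through.** The plan states no power or error rate for these tests, so there is no figure to reproduce. The check has five steps.

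**1. What each test covers**

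| Data | Planned test | Across arms? | Uses baseline? |
|---|---|---|---|
| Haematology, continuous | paired t/Wilcoxon | no | yes |
| Haematology, normal/abnormal | McNemar | no | yes |
| Vital signs | paired t/Wilcoxon, McNemar | no | yes |
| Chemistry, continuous | Kruskal-Wallis | yes (inferred) | no |
| Laboratory abnormality rates | Fisher, Section 8.6 | yes, five groups | only through some grades |

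No row is a contrast of change between a vaccine arm and placebo.

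**2. Within-arm tests when the vaccine has no effect**

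Inputs: n=25 per vaccine arm and n=20 placebo (Section 4.4). Assumptions: two-sided 5% level (the SAP states none for safety tests), and a shift d common to all arms, in SDs of the change, of 0.2, 0.3 or 0.5.

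Formula: P(reject) = P(|T| > t(0.975, n-1)), where T is noncentral t with n-1 df and noncentrality d√n. For d=0.3 and n=25 the noncentrality is 0.3 × 5 = 1.5.

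| d | Vaccine arm p<0.05 | Placebo p<0.05 | At least one of four vaccine arms | Named vaccine arm yes, placebo no |
|---|---|---|---|---|
| 0.2 | 16% | 14% | 50% | 14% |
| 0.3 | 30% | 25% | 76% | 23% |
| 0.5 | 67% | 56% | 99% | 29% |

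For d=0.3: 1 - (1 - 0.302)^4 = 0.763, and 0.302 × (1 - 0.247) = 0.227. The chance that at least one vaccine arm is significant while placebo is not is 0.763 × 0.753 = 57% (43% at both d=0.2 and d=0.5).

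**3. The same data compared between arms**

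In a two-sample test on change, 25 v 20, the common shift cancels, so the error rate is 5% for any d. Power is 37%, 74% and 90% for true differences of 0.5, 0.8 and 1.0 SD. The 95% CI half-width is t(0.975, 43) × √(1/25 + 1/20) = 2.017 × 0.3 = 0.605 SD. Estimates with intervals will therefore tell the reader more than p-values.

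**4. Chemistry with and without baseline**

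Simulation: five groups (25/25/25/25/20), all vaccine arms shifted 0.5 SD from placebo, 4,000 runs, baseline correlation assumed. Kruskal-Wallis on follow-up values has 29-31% power. On change it has 29%, 49%, 67% and 95% for correlations of 0.5, 0.7, 0.8 and 0.9. The gain is nil at 0.5 and large at 0.8 or above.

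**5. Percentage change in temperature**

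Using bounds from the fever grading in Table 18, a rise from 38.0 to 40 °C is 2/38 = 5.3%. The same rise from 100.4 to 104 °F is 3.6/100.4 = 3.6%. A percentage of a scale with an arbitrary zero has no fixed meaning.

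**The case against.** A reader might infer that the plan has no between-group laboratory test at all. That is wrong: the Fisher test in Section 8.6 covers haematology and chemistry, includes placebo, and runs by visit and overall. It also carries some baseline information, since creatinine grades include "OR increase of > 0.3 above baseline" and haemoglobin has a change-from-baseline criterion. It remains an omnibus test on rates, with no vaccine-versus-placebo estimate and no place in the shells.

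A reader might also infer that post-dose-2 chemistry change is left unspecified. Sections 8.3.1 and 8.6 and Listing 9A all provide for it at Day 36. The row in Tables 65-68 is a labelling error.

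A third tempting inference is that these p-values could misdirect the choice of formulations. The SAP does not support it. Of Tables 60-80, the interim report (Section 6.6.1) includes only 60 and 64. The DSMB reviews unblinded safety data with no p-value rule. The primary laboratory endpoint (Section 3.2.1) counts clinically significant results by severity and relatedness, which the continuous tests do not analyse, and vital signs are not among the primary endpoints.

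Placebo results would also be displayed beside the vaccine arms, and boxplots of change by group are planned, so a careful reader could see a shared shift. That limits the harm but does not justify printing p-values that invite the opposite reading. Finally, baseline adjustment by ANCOVA conflicts with Section 6.4 as written, so it needs an explicit exception.

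**Conclusion.** The point holds in this form: continuous haematology and vital signs are tested only within arm, continuous chemistry is tested without baseline, and the one between-group laboratory test addresses abnormality rates and is missing from its tables. Under an assumed common shift of 0.2 to 0.5 SD and no vaccine effect, within-arm testing marks a vaccine arm significant in 16% to 67% of cases. The loss of precision for chemistry depends on an assumed correlation and is negligible at 0.5. Neither the shifts nor the correlations come from the SAP.

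Importance is modest. These are supportive outputs in a Phase 1 trial whose safety analysis is mainly descriptive, and arm-level change with 95% CIs is shown in any case. The Day 36 label and the temperature metric are plain shell errors that need none of these assumptions.

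**What to change.** - Remove the paired and McNemar p-values from Tables 61-63 and 71-80, and the Kruskal-Wallis p-values from Tables 65-68.
- In their place, report each vaccine-minus-placebo difference in change from baseline with a 95% CI. Alternatively, take it from an ANCOVA of the post-vaccination value on group and baseline, on the log scale for ALT, AST and bilirubin, with a stated exception in Section 6.4.
- Add a row to Tables 60 and 64 for the Fisher result promised in Section 8.6.
- In Tables 65-68, relabel the change row after Visit 4 as Day 36 versus baseline.
- In Tables 79-80, report temperature change in °C, not percent.

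The data are already collected. The cost is shell and programming edits, plus a one-line amendment to Section 6.4 if ANCOVA is chosen. Simple differences in change need no such amendment.
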